## 8. Research Setting

The research would be conducted in the NICU at the University of New Mexico Hospital (UNMH). Patients would be identified after admission to the NICU. The application of the NIRS would occur in the NICU as well.

### **10. Prior Approvals**

The departmental approval has been obtained and is uploaded for review.

### **11. Multi-Site Research – N/A**

### **12. Study Procedures**

Any infant that is born at <32 weeks' gestational age and does not meet exclusion criteria as described above will be considered for the study. The mother/guardian must speak English as we do not have the resources to translate the documents, nor could we obtain consent appropriately. If an infant is born at another hospital and transferred to UNMH, they will be considered for the study only if the mother/guardian is physically present.

The study will be described following the consent script (attached) and if consent is obtained, the infant will then be given a study identifier (ex. NIRS-1). The "NIRS-1" component of the identifier will be the infant's number used so that identifying information can be removed. For sub-analysis, the infants will be divided into 3 groups to assess the impact of gestational age on the measurements. Specifically, the 3 groups will be divided into the following ages: Group 1: 23 to ≤26 weeks' gestation; Group 2: >26 weeks' gestation to ≤29 weeks' gestation; Group 3: >29 weeks' gestation to 31 6/7 weeks' gestation.

The NIRS device will be applied after the infant is admitted to the Newborn Intensive Care Unit (NICU) at UNMH (ideally within the first 12 hours of life). The device will remain in place, with routine skin care management during care times, for the first 96 hours of life and then removed. This will allow 72-96 hours of data collection, depending on the timing of the placement of the NIRS device in relation to the birth time. The SpO2 (routine oxygen saturation monitoring) information will be collected at the same time so that the relative cerebral fractional tissue oxygen extraction can be calculated. The data output will not be visible to the clinical team, so there will not be any incidental clinical interpretation of this data.

To apply the device, a trimmed piece of Mepitel (MoInlycke), which is a translucent skin dressing, will be placed with the hydrocolloid adhesive-backed NIRS sensor placed

PROTOCOL TITLE:

directly onto the Mepitel. The sensor will then be placed with the skin dressing onto the central forehead of the infant. The sensor will be plugged in to ensure that signal strength is appropriate. There will be daily inspection of the sensor site by the research team, with the area monitored by the bedside nurse with each care-time (usually every 3 hours). The area will be monitored for erythema or irritation of the skin around the sensor, and the sensor will be removed or replaced if necessary. We will avoid lifting up the sensor unless necessary for removal or repositioning. Care will be taken to avoid pressure on top of the sensor. After the infant is 96 hours of age, the sensor will be removed. Adhesive remover or a warm moist cloth will be used to slowly remove the sensor from the skin. The sensor will then be discarded after use. The NIRS probe (circled in red) is shown below in this sample image taken from van Bel, et al[6]. Additionally, the NIRS probe is plugged into a NIRS monitor, which is then plugged into the Phillips monitor if desired. We currently have 6 of the devices which connect the NIRS to the Phillips monitor, however need to purchase the NIRS monitor and the NIRS probes.

Information will be collected from the medical record at time of enrollment as well as at the time of infant discharge. This information will include: gestational age at birth, birth weight, mode of delivery, sex of infant, maternal complications during pregnancy (including pre-eclampsia, chorioamnionitis, hypertension, diabetes, thyroid disease, and cervical insufficiency), maternal medications during pregnancy, resuscitation required at birth including if chest compressions were done, length and type of respiratory support infant required, intraventricular hemorrhage, necrotizing enterocolitis, patent ductus arteriosus and if treatment was used, chronic lung disease, retinopathy of prematurity, any surgeries that were completed during the hospitalization, sepsis, hospital length of stay, time to full volume nipple of feeds, and death if applicable. The data obtained during the NIRS recording will be collected and analyzed to determine the average cerebral regional oxygen saturation. The relative cerebral fractional tissue oxygen extraction will be calculated. The blood pressure and heart rates of each infant that are normally obtained for clinical purposes will be extracted from the patient charts during the time of the NIRS monitoring.

PROTOCOL TITLE:

### **13.Data Analysis**

The cerebral regional oxygen saturation data will be averaged for each infant. All male and female data will be analyzed separately and the compared to determine any statistical differences that are present between sexes. NIRS parameters will be summarized as median and interquartile ranges. The relative cerebral fractional tissue oxygen extraction will be calculated using the following equation:  $(SpO_2 - rScO_2)/SpO_2$ .

As described above, there will be a sub-analysis of the infants enrolled based on gestational age. Specifically, the 3 groups will be divided into the following ages: Group 1: 23 to  $\leq 26$  weeks' gestation; Group 2:  $>26$  weeks' gestation to  $\leq 29$  weeks' gestation; Group 3:  $>29$  weeks' gestation to 31 6/7 weeks' gestation. Comparisons among different groups will be analyzed by one-way ANOVA followed by Dunn's method. Categorical data will be analyzed using Fisher's test. Spearman's rank correlation coefficient will be used to calculate correlations between cerebral regional oxygen saturation, relative cerebral fractional tissue oxygen extraction and gestational age. Values of  $p < 0.05$  will be considered statistically significant.

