## 2. Background

Near-infrared spectroscopy (NIRS), is a technology that can provide continuous, non-invasive monitoring of oxygenation in tissue[1]. Light absorption is measured at a few discrete wavelengths which can provide information for the tissue oxygen saturation in multiple organs[2], with cerebral, renal and splanchnic oxygenation being the most commonly measured in neonates[1]. NIRS technology was first available in 1977, however different sensors and manufacturers resulted in a large range of regional oxygen saturation (RSO2), making it difficult to establish normative values within a specific population[1]. Thus, improvements in the technology has resulted in the ability to consider more clinical uses for the NIRS technology.

Infants with congenital heart disease is a population in which the NIRS technology has been applied. The use of cerebral oximetry measurement has provided the first indication of a clinical problem in 23% of the procedures in which the technology was utilized[1]. While some initial studies have shown a negative correlation between cerebral regional oxygen saturation (cRSO2) and gestational age[3], routine use in the preterm infant has not been established.

Infants born prematurely (<37 weeks’ gestation), and especially those born extremely preterm (<28 weeks’ gestation), have organs that are immature and vulnerable. There are fluctuations in cerebral blood flow due to limitations in autoregulation, which may be exacerbated by routine care of the infant[4]. Previously there was a limitation in the ability to monitor these changes in blood flow and saturations, however NIRS now provides the technology needed. There are clinical trials ongoing to assess cRSO2 immediately after birth in an attempt to improve outcomes[5] as well as monitoring in the first 72 hours of life in extremely preterm infants[4]. While these studies will likely provide support for applying NIRS as routine care for preterm infants, there is data lacking when infants are born at altitude. It is unknown if the increased altitude in places such as Albuquerque and Denver would result in a different range of expected values with NIRS monitoring. Thus, we proposed a prospective observational study in which we apply NIRS monitoring to

PROTOCOL TITLE:

infants born <32 weeks' gestation for the first 96 hours of life to assess the cRSO2 as well as outcome information for the infant.

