### **3. Study Design**

The study will be a prospective observational study, in which any infant consented to participate in the study will have the NIRS applied for the first 96 hours of life. It will be the goal to apply the NIRS sensors in the first 12 hours of life. All infants will have the same treatment if in the study, but clinicians will not be able to see the data obtained so that there is no clinical interpretation during this time.

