#### Exclusion Criteria:

- Any known cardiac anomaly or other anomaly which may impair perfusion and blood flow.
- Infant born after placental abruption or concern for extreme blood loss immediately after birth.
- Unable to consent the mother/guardian due to maternal health issues after delivering (eg requiring intubation or sedation after the delivery).
- Mothers/guardians that are prisoners, as the study team would like to have continuing communication with the mother during the study period as needed.
- Mothers/guardians that are <18 years of age will not be approached for consent.
- Any mother/guardian that is not able to consent due to having a legal representative will not be approached for consent in this study.
- Any infant that is planned to be placed for adoption
- Infant is greater than 24 hours of age at time of consent.

Individuals will be screened for eligibility by reviewing the Newborn Intensive Care Unit (NICU) census twice daily.

Any infant that has been consented for participation and completes at least 48 hours of NIRS monitoring will be included in the final study sample.

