## 6. Study Timelines

An individual will participate in the study if the guardian consents for participation. The NIRS device will be applied after consent has been obtained (ideally within the first 12 hours of life). The device will remain in place, with routine skin care management during care times, for the first 96 hours of life and then removed. No further interventions will occur during the study period. Data on relevant outcomes will be extracted from the hospital chart during the birth hospitalization.

The duration of time to enroll subjects is 2 years. If the goal enrollment is reached sooner, then enrollment will be stopped. Upon completion of enrollment, data will then be analyzed. This is expected to be completed 6 months after enrollment is complete; thus, the study duration is expected to be 2.5 years.

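### Each infant's average cRSO2 is not aligned on postnatal age, so comparisons may be confounded by when the recording started and ended

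*Combined protocol and SAP*

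**What the plan says.** **Summary measure.** Section 13 states: "The cerebral regional oxygen saturation data will be averaged for each infant". Gestational-age groups are compared by one-way ANOVA followed by Dunn's method, and Spearman correlations are planned. The section has no time bins, no common window, and no term for postnatal age or placement time.

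**Start of recording.** Section 3 sets a target: "It will be the goal to apply the NIRS sensors in the first 12 hours of life". Section 6 gives the order of events: "The NIRS device will be applied after consent has been obtained (ideally within the first 12 hours of life"). The only firm limit is an exclusion criterion in Section 4: "Infant is greater than 24 hours of age at time of consent". That limits age at consent. No maximum interval from consent to placement is given.

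**End of recording.** Section 12 fixes an age, not a duration: "After the infant is 96 hours of age, the sensor will be removed". Section 4 takes consented infants with at least 48 h of monitoring into the final sample, without saying which 48 h. Sections 15 and 18 keep the data from recordings that stop early.

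**Expected yield.** Section 12 states: "This will allow 72-96 hours of data collection, depending on the timing of the placement of the NIRS device in relation to the birth time".

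**Use of the average.** Section 1 hypothesises lower values than the normative ones already described. Aim 2 relates each infant's average, and its fluctuation, to outcomes that include death. Section 13 names no reference value, reference window or test for the sea-level comparison.

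**The concern.** Aim 1 is about cRSO2 over the first 96 hours of life, but a whole-recording average describes whichever part of that period was recorded. If cRSO2 changes with postnatal age, two infants with the same course can have different averages only because their sensors went on or came off at different ages.

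Three comparisons are exposed:

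- **Gestational age:** if start or end times differ between the three groups, part of any group difference may reflect timing.
- **Aim 2:** an infant who dies after 48 h of recording but before 96 h of age contributes a shorter average weighted to earlier hours. The outcome then helps to determine the exposure window.
- **Sea level:** an average over a floating window can be set against a published value only if that value covers the same ages.

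**Working it through.** **1. The stated yield.** Length of recording = 96 h minus age at placement. Placement at 0 h gives 96 - 0 = 96 h, and placement at 24 h gives 96 - 24 = 72 h. This reproduces 72-96 h, but only for placement between 0 and 24 h of age. The upper end needs placement at birth, before NICU admission and consent. Consent at 24 h followed by any placement delay gives less than 72 h. Section 4 accepts 48 h.

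**2. Ages covered by the average.** For a recording from age a to age b, mean postnatal age = (a + b)/2, and first-day share = max(0, 24 - a)/(b - a). The 6 h start is illustrative and does not come from the documents.

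| Window (h of life) | Length (h) | Mean age (h) | Share from first 24 h |
|---|---|---|---|
| 0-96 (theoretical limit) | 96 | 48 | 24/96 = 25% |
| 6-96 | 90 | 51 | 18/90 = 20% |
| 12-96 | 84 | 54 | 12/84 = 14% |
| 24-96 | 72 | 60 | 0% |
| 6-54 | 48 | 30 | 18/48 = 37.5% |
| 24-72 | 48 | 48 | 0% |

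The end of the window can matter more than the start. Start times of 0 and 24 h, both running to 96 h, separate the mean ages by 60 - 48 = 12 h. The 48 h rule as written also admits 0-48 h and 48-96 h, with mean ages of 24 and 72 h, a gap of 48 h. That pair is an extreme, since it needs placement at birth in one infant and a long delay after consent in the other.

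**3. Effect on one infant's average.** Let first-day cRSO2 differ from later values by D points. The documents give no value, so D = 3, 5 and 10 are assumptions.

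- 6-96 h against 24-96 h: 0.20 × D = 0.6, 1.0 and 2.0 points.
- 6-54 h against a window starting at 24 h: 0.375 × D = 1.1, 1.9 and 3.8 points.

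**4. Effect on the gestational-age contrast.** Assume a linear drift of g points per 24 h and windows ending at 96 h. A difference of h hours in mean start time moves mean age by h/2, so bias = g × h/48. For g = 1, 2, 4 and 6:

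- h = 6: 0.13, 0.25, 0.5 and 0.75 points.
- h = 12: 0.25, 0.5, 1.0 and 1.5 points.

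For scale, take about 33 infants per group (100/3) and an assumed SD of 5 or 8 points. The difference detectable with 80% power at two-sided 5% is (1.96 + 0.84) × SD × √(2/33), about 3.5 or 5.5 points. A bias of 0.5 points raises the false-positive rate of a pairwise contrast from 5% to 6.9% (SD 5) or 5.7% (SD 8). A bias of 1.5 points raises it to 23% or 12%. If start and end times do not differ between groups, this bias is zero.

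**5. Effect on the external comparison.** Section 13 specifies no test, so suppose 100 infants are compared with a fixed value. The standard error is SD/√100 = 0.5 or 0.8 points. A window mismatch worth 0.5 points gives a false-positive rate of 17% or 10%, and one worth 1.0 point gives 52% or 24%.

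**The case against.** A whole-recording average is a legitimate descriptive summary for a pilot observational study, and choosing epochs is partly a matter of preference. Confounding needs two things: cRSO2 must change over the first 96 h, and windows must differ between groups, with outcome, or from the reference. The documents show neither. Section 2 describes fluctuating cerebral blood flow from limited autoregulation, which is not a trend with postnatal age. Under the drifts assumed above, the start-time bias between gestational-age groups is at most 1.5 points, below the detectable difference. All of this stands, and it limits the point to a possibility.

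Several stronger readings are tempting and are not supported:

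- A reader might infer that the planned contrasts are already partly contrasts of placement time. That states as fact what depends on both conditions.
- A reader might infer that late placement is systematically linked to sicker infants. The documents do not show this. Mothers too unwell to consent are excluded, and transferred infants face the same 24 h consent limit.
- A reader might infer a definite mismatch with sea-level data, because Section 2 mentions work immediately after birth "as well as monitoring in the first 72 hours of life in extremely preterm infants". Those trials are cited as ongoing and are not named as the source of the normative values. The reference window is unknown, so a mismatch can be neither asserted nor ruled out.
- A reader might count altitude and sea level as two contrasts. In this single-site study they are one external comparison.

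The stated 72-96 h is also only what the schedule is said to allow, and consent at exactly 24 h falls short of 72 h only by the placement delay. The inconsistency is small, but the passages still need to agree.

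The objection does not remove the structural fact: the averages cover different ages, and nothing in Section 13 aligns them.

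**Conclusion.** The point holds as a possible source of confounding that is cheap to prevent. The text establishes that the averages are not aligned on postnatal age, with a first-day share that runs from 0% to 20% on recordings to 96 h (for starts from 6 h) and reaches 37.5% on a 6-54 h recording. The consequences rest on assumption: 0.6 to 3.8 points between individual infants for D of 3 to 10, and up to 1.5 points between gestational-age groups for drifts up to 6 points per 24 h and mean start times 12 h apart. The sea-level comparison is the most sensitive, because the mean of 100 infants is precise enough for a shift of 1 point to matter. The documents do not show that any of these biases is present.

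**What to change.** **Section 13**

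- Summarise cRSO2 as median and IQR by postnatal-age epoch: 0-24, 24-48, 48-72 and 72-96 h of life.
- Base the gestational-age and Aim 2 comparisons on these age-aligned values, either epoch by epoch or through a repeated-measures model with postnatal age that uses all data, including short recordings.
- Keep the whole-recording average as a secondary summary.
- Compare with sea-level values only over the same postnatal-age window as the reference, and name that reference.

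A single common window such as 24-72 h is a weaker choice. It drops 90 - 48 = 42 of the 90 h in a 6-96 h recording, and a 6-54 h recording fills only 54 - 24 = 30 of its 48 h.

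**Section 12**

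- Add age at sensor placement and at removal to the data collected.
- Reconcile the stated 72-96 h with placement after consent (Section 6), consent up to 24 h of age and the 48 h rule (both Section 4). The use of partial recordings in Sections 15 and 18 should be squared with the 48 h rule at the same time.

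**Cost.** A little more analysis, two extra recorded times, and fewer infants in the 0-24 h epoch. No extra monitoring of the infants is needed.

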### **5. Number of Subjects**

PROTOCOL TITLE:

This is a single site, observational study. The goal number of patients to be recruited is 100. A similar study that evaluated an older cohort (30 weeks' gestation to 42 weeks' gestation) was able to find significant differences with a sample size of 100[3]. Given the number of extremely preterm infants (<28 weeks' gestation) born at UNMH varies from 18-30 per year, we expect to reach goal enrollment within a 2-year period, as we are including up to 32 weeks' gestation.

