### **20. Recruitment Methods**

Any infant that meets the inclusion / exclusion criteria will be considered for enrollment. The mother / guardian will be approached by one of the study personnel that are included on this IRB, and the study will be discussed if they are interested in the study. The consent script has been included to show what the study personnel would verbally state to the mother / guardian. The mother / guardian may be approached at the infant's bedside or in her hospital room. If approached at the infant's bedside, the mother / guardian will be given the option to go into a family room to discuss the study further for additional privacy. The Powerchart census will be reviewed twice daily to monitor for admission of infants that would meet criteria. There will be no additional recruitment materials used for this study.

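### Twins and higher multiples can all be enrolled, but the gestational-age tests treat infants as independent, so those p-values are somewhat too small if siblings' cRSO2 is positively correlated

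*Combined protocol and SAP*

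**What the plan says.** **Who can enter.** Section 4 admits infants born before 32 weeks. None of its criteria concerns twins or higher multiples, and none allows only one infant per mother. Section 12 says that an infant under 32 weeks who "does not meet exclusion criteria as described above will be considered for the study", and Section 20 adds: "Any infant that meets the inclusion / exclusion criteria will be considered for enrollment". By Section 4, a consented infant who "completes at least 48 hours of NIRS monitoring will be included in the final study sample".

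**How they are analysed.** The unit in Section 13 is the infant: "The cerebral regional oxygen saturation data will be averaged for each infant". For the three gestational-age groups, "Comparisons among different groups will be analyzed by one-way ANOVA", followed by Dunn's method. Spearman's coefficient relates cRSO2, fractional oxygen extraction and gestational age. Fisher's test is used for categorical data, and males are compared with females. The threshold is p < 0.05. The section has no mixed model, GEE, clustered variance, one-per-family rule or sensitivity analysis.

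**What is recorded.** The chart items in Section 12 begin with "gestational age at birth, birth weight, mode of delivery, sex of infant, maternal complications during pregnancy". Neither plurality nor a family identifier is on that list. Section 16 gives each infant a running number. It removes date of birth and record number from the data and keeps the link to identifiers in a separate file. Section 37 says identifying information is destroyed when the study ends.

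**Sample size.** In Section 5, "The goal number of patients to be recruited is 100". The only support is that a study in an older cohort "was able to find significant differences with a sample size of 100".

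**The concern.** Siblings from one pregnancy share the mother, her complications and medications, and the gestational age at birth. They therefore always fall in the same gestational-age group and have the same value in the Spearman correlation. Where siblings' cRSO2 values are positively correlated, a second twin adds less than a full infant's worth of information about gestational age, but the named tests count it as a full one. Their null distributions are then too narrow.

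At stake is the claim that cRSO2 or oxygen extraction differs by gestational age at this altitude. Gestational age is the only explanatory variable that Section 13 names for both a group comparison and a correlation, and a significant result would be accepted more often by chance than the stated 5%. If nothing in the de-identified data shows which infants are siblings, the error may also be impossible to correct once identifiers are destroyed.

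**Working it through.** **The plan's own figure.** The target of 100 infants cannot be reproduced, because Section 5 gives no effect size, standard deviation, power or clustering allowance. It serves here only as the number of infants.

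**Inputs.** From the documents: N = 100 (Section 5) and alpha = 0.05 (Section 13; two-sided is assumed, as sidedness is not stated). Assumed, because the documents give neither: the share of infants in twin pairs, f = 15-35%, and the sibling correlation in cRSO2, ICC = 0.3-0.7.

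**Tests on gestational age (predictor fully shared by siblings).**
- Design effect: DE = 1 + f × ICC
- Effective sample: 100 / DE
- Actual alpha, one-df test (Spearman, roughly): 2 × [1 − Φ(1.96 / √DE)]
- Actual alpha, three-group comparison (two df, large-sample): exp(−5.991 / (2 × DE))

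| f | ICC | DE | Effective N | Alpha, one df | Alpha, two df |
|---|---|---|---|---|---|
| 15% | 0.3 | 1.045 | 95.7 | 5.5% | 5.7% |
| 30% | 0.5 | 1.150 | 87.0 | 6.8% | 7.4% |
| 35% | 0.7 | 1.245 | 80.3 | 7.9% | 9.0% |

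Worked for the last row: DE = 1 + 0.35 × 0.7 = 1.245; 100 / 1.245 = 80.3; 1.96 / √1.245 = 1.757, a two-sided probability of 7.9%; exp(−5.991 / 2.49) = 9.0%.

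**Simulation check (N = 100, no true effect, at least 5,000 studies per setting).**
- No twins: ANOVA 4.9%, Spearman 5.2%.
- f = 30%, ICC = 0.5: ANOVA 6.8-8.1%, Spearman 6.4-7.0% over four runs.
- f about 35%, ICC = 0.7: ANOVA 8.8-9.1%, Spearman 8.2%.
- f = 40%, ICC = 0.7, just outside the assumed range: ANOVA 9.5%, Spearman 8.1%.

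**Aim 2 and the cRSO2-extraction correlation (predictor specific to the infant).** The factor is about 1 + f × ICC_x × ICC_y. With both correlations equal:
- Low end: 1 + 0.15 × 0.3 × 0.3 = 1.014, alpha 5.2%.
- High end: 1 + 0.35 × 0.7 × 0.7 = 1.172, alpha 7.0%.

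Simulated Spearman tests between two infant-level variables gave 5.2% (f = 16%, ICC 0.3), 6.1% (f = 24%, ICC 0.5) and 7.1% (f = 34-36%, ICC 0.7).

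**Male-female comparison (simulated t-test, f = 30%, ICC = 0.5).** Actual alpha was 3.5% if all pairs are opposite-sex, 5.3% if half or 65% are same-sex, and 6.5% only if all are same-sex.

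**The case against.** The strongest reply concerns scope and size.

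- **Direction.** A reader might infer that every planned test is too liberal. That does not follow. Opposite-sex pairs make the male-female comparison conservative, and mixed pairs leave it near nominal.
- **Aim 2.** A reader might carry the gestational-age penalty over to Aim 2. But Aim 2 sets outcomes against each infant's own average and fluctuation in cRSO2, which siblings do not share exactly, so the penalty is smaller. Section 13 also names no specific model for Aim 2.
- **Confidence intervals.** It is tempting to say that intervals will be too narrow. The plan specifies none, only medians, interquartile ranges and p-values.
- **Main objective.** The range of cRSO2 at altitude is to be described, and clustering hardly disturbs a median or interquartile range. The three-group comparison is labelled a sub-analysis, and the funding section calls the study a pilot.
- **Assumed inputs.** At the low end of the assumed range the effect is negligible (5.5%, with 96 effective infants), and nothing in the documents favours the upper end.
- **Unseen attachment.** Section 16 refers to a spreadsheet of further variables that is not in the text, so a plurality field cannot be ruled out.
- **Model stability.** With most birth sets of size one, a random-intercept variance would rest on few pairs, and rare outcomes may not support a GEE.

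All of these stand as limits. None removes the core: siblings are eligible, they share gestational age exactly, and Section 13 as written would use no family field even if one were collected.

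**Conclusion.** The point holds for the gestational-age ANOVA with Dunn's method and the Spearman correlations with gestational age. The direction there requires only a positive sibling correlation. The size is modest and rests on assumed values: with 15-35% of infants in twin pairs and a correlation of 0.3-0.7, the design effect is about 1.05-1.25, the effective sample about 80-96, and actual alpha about 5.5-8% for a one-df test. The three-group ANOVA reaches about 9% at the upper end; 9.5% needs about 40% in pairs. Aim 2 and the cRSO2-extraction correlation run at roughly 5-7%.

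The documents do not support reading this as a flaw in every test or in the descriptive range of cRSO2. It should be corrected because, if multiples enrol, the plan as written gives gestational-age p-values that are too small, and the remedy is cheap while sibling links can still be recorded.

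**What to change.** 1. **Data (Sections 12 and 16).** Record plurality and a coded birth-set (mother) number, and keep that code in the de-identified dataset so that it survives the destruction of identifiers.
2. **Analysis (Section 13).** State that multiples are eligible. Analyse the gestational-age comparisons with standard errors clustered on mother, by GEE or a mixed model. If the rank tests are kept, take their p-values from a permutation or bootstrap by mother.
3. **Sensitivity check.** Repeat the gestational-age analyses with one randomly chosen infant per birth set, and apply the same check to the sex and Aim 2 comparisons. For rare outcomes, where a clustered model may not be stable, this check may be all that the data support.
4. **Reporting.** Give the number of birth sets alongside the number of infants.

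The cost is a coded field and a plurality entry, a little more code and slightly larger p-values. No extra procedures are needed. The target of 100 need not change; matching the information of 100 independent infants on gestational age would take about 105 to 125 (100 × 1.045 to 100 × 1.245) under the same assumptions.
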